Suppose a patient suspected of lung cancer has a negative result of the bronchoscopic procedure. In that case, a surgical procedure (mediastinoscopy or lobectomy/pneumectomy with lymph node dissection) could follow to obtain tissue. This surgical procedure will be performed regardless of the result of nCLE imaging. If a surgical procedure is indicated, we will collect the histological images to compare with nCLE imaging. This study will not interfere with the standard cytology or the standard histology process. Digital copies of the cytological and histological slides of the measured nodules will be obtained and compared with the frames of the nCLE sequences.

Final Diagnosis or Definitive Diagnosis

For this 12-month analysis, pathology results of Robotic-aided biopsy samples that will be diagnostic of a non-malignant condition or indeterminate will be referred to as negative for malignancy or negative for brevity. Follow-up will be conducted to determine the final diagnosis (malignant or non-malignant). All cases will be followed according to the practitioner's judgment and standard of care testing (e.g., surgical tissue biopsy, repeat Robotic, CT-guided transthoracic needle biopsy or aspiration (TTNA), serial CT imaging, and lung health visits). Cases with subsequent diagnostic tests confirming a non-malignant diagnosis or without lesion progression on radiographic follow-up will be considered true-negative at 12 months, consistent with prior Robotic studies. If the follow-up diagnostics reveal malignancy or lesion growth on repeat imaging with appropriate follow-up diagnostic testing, this will be considered a false-negative. The following will also be regarded as false-negative: death due to lung cancer within 12 months; treatment without a confirmed diagnosis; and new diagnosis of cancer in the lung from any site (including non-index lesions or lymph nodes diagnosed as malignant by linear bronchoscopy during or after the index procedure).

Twelve-month diagnostic yield will be calculated per subject as the rate of true-positives (for malignancy) plus true negatives (for malignancy) of all subjects with attempted lung lesion biopsies.

Adverse Events

Definitions

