The tumor board will determine intermediate diagnosis and management recommendations for each patient at the intermediate and final diagnosis phases (see Figure 3). Three therapeutic management options will be considered: "neither treatment nor follow-up", "follow-up", or "treatment" (see above). If the diagnosis is certain, "neither surgery nor surveillance" will be recommended for benign nodules; treatment will be recommended for malignant lesions; either treatment or follow-up will be recommended for indeterminate nodules.

An intermediate diagnosis and an intermediate management recommendation will be provided after the tumor board receives TBNA histological results and recorded in the Case Report Form for each patient of both arms.

A final diagnosis and a final management recommendation will be provided just after the final diagnosis results are received by the tumor board and recorded in the Case Report Form for each patient of both arms.

These intermediate diagnosis and management recommendations will also be compared to the definitive diagnosis and final patient management decisions.

7. Statistical Analysis

Population demographics comparison in both arms:

Statistical analysis will be performed to compare the patient population in terms of demographics to assess whether there are any differences between the populations of the two arms in terms of age, sex, race, type of lung cancers, and cancer prevalence.

Lesion characteristics comparison in both arms:

Statistical analysis will be performed to compare the lesion characteristics to assess whether there is any difference in lesion characteristics between the two arms, in terms of size, location of the nodule, Presence of bronchus sign on computerized tomography, lung zone, positive PET, associated lymphadenopathy, distance closest to fissure, distance from lesion to pleura, and pre-procedure probability of malignancy.

Navigation Accuracy

Distance between the tip of the locatable guide/nCLE Confocal MiniprobeTM and the targeted lung lesion will be measured for each nodule. The median and standard deviation of the distance will be calculated for both arms. Using a statistical test (Student T-test), they will be compared between arms (Robotic-guided TBNA and Robotic-nCLE-guided TBNA).

Navigation success

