- PPV: Probability that malignancy is present when sequential cumulative ROSE passes is positive: $= a/(a + b)$
- NPV: Probability that malignancy is not present when sequential cumulative ROSE passes is negative: $= d/(c + d)$

The same calculations will be performed for the different sequential cumulative nCLE passes. Diagnostic performances for both techniques will be compared using the DeLong and DeLong statistical method [26] with the final diagnosis as the reference diagnosis.

Per patient diagnostic yield (cumulative pass diagnostic yield) and performance calculations

Per patient diagnostic yield of each bronchoscopic procedure (Robotic-guided TBNA and Robotic-nCLE-guided TBNA) is defined as the proportion of patients whose procedure will yield a definitive diagnosis out of the total number of patients that have received that procedure. Two diagnostic yields will be calculated: one for the Robotic-guided TBNA arm and one for the Robotic-nCLE-guided TBNA arm. 95% confidence intervals will be calculated, and the p-value to compare diagnostic yield values between arms.

The diagnostic accuracies of a bronchoscopic procedure (Robotic-guided TBNA and Robotic-nCLE-guided TBNA) will be measured at the end of a follow-up period according to their sensitivities and specificities. The sensitivity test will measure the ability of a technique to correctly identify those patients with the disease (true positive rate). In contrast, the specificity test will measure the ability of the technique to correctly identify those patients without the disease (true negative rate). Sensitivity, specificity, positive predictive value (PPV), and negative predictive value (NPV) will be calculated as the accuracy of the Robotic-guided TBNA and that of Robotic-nCLE-guided TBNA diagnosis (based on final pathology results) compared to the definitive diagnosis based on all available procedures and follow-up.

Where a = true positive, b = false positive, c = false negative, and d = true negative:

- Sensitivity: Probability that a Robotic-guided biopsy will be positive when malignancy is present (true positive rate): $= a/(a + c)$
- Specificity: Probability that a Robotic-guided biopsy will be negative when malignancy is not present (true negative rate): $= d/(b + d)$
- PPV: Probability that malignancy is present when a Robotic-guided biopsy is positive: $= a/(a + b)$
- NPV: Probability that malignancy is not present when a Robotic-guided biopsy is negative: $= d/(c + d)$

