- 3) the continuous movement of a part of the cells in one direction ('directional streaming')

These criteria will be evaluated qualitatively.

New nCLE characteristics in malignant and benign lung lesions could also be identified during this study. An imaging atlas of nCLE images will also be built for the different tumor types on in-vivo characteristics. The department of pathology will be strongly involved in this project.

nCLE-video images will be reviewed and diagnosed retrospectively, independently, and blindly by investigators, expert readers, and pathologists.

The diagnostic yield will be tested to give the likelihood that nCLE will provide the information needed to establish a diagnosis.

Correlation analysis will also be performed between:

- nCLE imaging results and digital images of cytological or histopathological results
- nCLE imaging results in different tumor types.

8. End Points

Primary endpoint: The definitive diagnosis will serve as the reference standard for the calculation of study endpoints. The study pathologists will not be aware of nCLE results. The primary endpoint of this study will be the first-pass diagnostic yield, as defined in the section "Sample size calculation", i.e. and is calculated as the proportion of patients for which first-pass TBNA during the bronchoscopic procedure yielded a definitive diagnosis out of the total number of patients that have received a diagnostic procedure

Secondary endpoint: The secondary outcome of this study will be the per-patient diagnostic yield, calculated as the proportion of patients in whom the bronchoscopic procedure yielded a definitive diagnosis out of the total number of patients that have received a diagnostic procedure.

Third endpoint: The third endpoint for patient management will be assessing the clinical impact of nCLE by determining the proportion of patients with a correct change in definitive diagnosis and the associated change in management plan with nCLE.

First-pass diagnostic yield:

The study is designed to enroll 118 patients who will be randomly assigned 1:1 to Robotic-guided TBNA alone or Robotic-nCLE-guided TBNA for a statistical power of 80% with a 2-sided significance level of 0.05 to detect an increase of the primary study endpoint (per pass TBNA diagnostic yield) of at least 20%, from 70% to 90%, between the Robotic-guided TBNA and the Robotic-nCLE-guided TBNA.

Per patient diagnostic yield (cumulative pass diagnostic yield) and performance:

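### Treatment without a confirmed diagnosis sets the reference status to malignant, and nothing keeps the nCLE read out of that decision, so nCLE and ROSE accuracy can be distorted

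*Combined protocol and SAP*

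**What the plan says.** All references are to the combined protocol and SAP.

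- **The rule.** Section 5, Final Diagnosis or Definitive Diagnosis: "The following will also be regarded as false-negative: death due to lung cancer within 12 months; treatment without a confirmed diagnosis". A false negative is a negative biopsy with a malignant reference status.
- **Where the reference is used.** Section 8, Primary endpoint: "The definitive diagnosis will serve as the reference standard for the calculation of study endpoints". Section 7 compares the diagnostic performance of ROSE and nCLE "with the final diagnosis as the reference diagnosis". In the final-diagnosis text of section 5: "Twelve-month diagnostic yield will be calculated per subject as the rate of true-positives (for malignancy) plus true negatives (for malignancy) of all subjects" with an attempted biopsy.
- **Treatment of uncertain nodules.** Section 6, Diagnostic and Therapeutic Management: "either treatment or follow-up will be recommended for indeterminate nodules". The treatments listed there include radiation and systemic therapy, which need not produce tissue. Follow-up is left to the practitioner's judgment (section 5).
- **Who knows the nCLE read.** The physician performing the procedure evaluates the images and judges whether malignancy is present (section 5, Steps during the procedure and Intra-procedure Interpretation of nCLE). On masking at the reference side, section 8 says only: "The study pathologists will not be aware of nCLE results".
- **What nCLE is expected to do.** The third endpoint is the proportion of patients with a "correct change in definitive diagnosis and the associated change in management plan with nCLE".
- **A partial safeguard.** Under Histological evaluation, surgery to obtain tissue after a negative bronchoscopy does not depend on the nCLE result.

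**The concern.** An accuracy analysis needs a reference that the test under study cannot influence. Here one route to a malignant reference status is a treatment decision rather than tissue or follow-up, and the plan leaves open that the nCLE read contributes to that decision. Where it does, nCLE helps to write its own reference (incorporation bias). The nodule enters the nCLE table as a true positive and the ROSE and TBNA tables as a false negative, with no evidence of cancer.

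At stake are nCLE specificity and PPV, which can be too high, and ROSE/TBNA sensitivity and NPV, which can be too low. The surgical safeguard does not close the path, because surgery to obtain tissue yields a confirmed diagnosis. The rule concerns patients treated without one.

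**Working it through.** **Inputs from the plan.** 59 patients per arm and malignancy prevalence 0.5 (section 4, Sample size calculation). 59 × 0.5 = 29.5, which agrees with the expected minimum of 29 malignant nodules per arm. The 59 itself reproduces with the unpooled formula: (0.7 × 0.3 + 0.9 × 0.1) × (1.95996 + 0.84162)² / 0.2² = 0.30 × 7.849 / 0.04 = 58.87, rounded up to 59. It is not in dispute. The plan gives no figure for how often patients are treated without confirmation.

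**Assumptions (illustration only).** In the nCLE arm, 30 nodules are truly malignant and 29 truly benign. nCLE detects 27/30 and clears 23/29, so it has 6 false positives. ROSE detects 24/30 and has no false positives. Of the 6 benign nodules with a positive nCLE read, k are treated without tissue and so become malignant in the reference.

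**Formulas (section 7).** Sensitivity a/(a+c), specificity d/(b+d), PPV a/(a+b), NPV d/(c+d). 12-month yield is (TP + TN)/59, taken here from the ROSE/TBNA result.

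| k | nCLE sensitivity | nCLE specificity | nCLE PPV | ROSE sensitivity | ROSE NPV | 12-month yield |
|---|---|---|---|---|---|---|
| 0 | 27/30 = 90.0% | 23/29 = 79.3% | 27/33 = 81.8% | 24/30 = 80.0% | 29/35 = 82.9% | 53/59 = 89.8% |
| 1 | 28/31 = 90.3% | 23/28 = 82.1% | 28/33 = 84.8% | 24/31 = 77.4% | 28/35 = 80.0% | 52/59 = 88.1% |
| 3 | 30/33 = 90.9% | 23/26 = 88.5% | 30/33 = 90.9% | 24/33 = 72.7% | 26/35 = 74.3% | 50/59 = 84.7% |

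nCLE sensitivity hardly moves. Each patient moved from true negative to false negative costs 1/59 = 1.7 points of yield; three cost 5.1.

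**A second set of assumptions.** The background cites 90% nCLE accuracy in tumors. Take that as sensitivity and specificity of about 0.9, with 29 malignant and 30 benign nodules: 26/29 and 27/30, so 3 false positives. Let TBNA find 23 of the 29. If all 3 false positives are treated without tissue, nCLE specificity goes from 27/30 = 90.0% to 27/27 = 100%, and TBNA sensitivity from 23/29 = 79.3% to 23/32 = 71.9%.

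**Ways of handling the k = 3 patients, first example.**

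| Handling | nCLE specificity | ROSE sensitivity |
|---|---|---|
| Counted malignant (the plan) | 23/26 = 88.5% | 24/33 = 72.7% |
| Left out | 23/26 = 88.5% | 24/30 = 80.0% |
| Counted benign | 23/29 = 79.3% | 24/30 = 80.0% |

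Leaving them out repairs ROSE sensitivity but not nCLE specificity, because the patients removed are the nCLE false positives. In the yield, relabelling them non-diagnostic changes nothing: like a false negative, such a patient stays in the denominator and out of the numerator.

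**First-pass yield.** Section 4 requires histological confirmation that matches the final diagnosis. An indeterminate first pass fails whether the nodule is later called malignant or not. Only a first pass that would have counted as a matching benign diagnosis can change, and section 6 does not recommend treatment when a benign diagnosis is certain.

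**The case against.** The strongest reply is that the pathway is inferred. No section says that the nCLE read reaches the tumor board. Section 6 ties the intermediate recommendation to TBNA histology, the procedure list labels nCLE acquisition as research, and surgery is kept independent of it. That stands: the plan leaves the path open but does not prescribe it. Against it, the third endpoint expects management to change with nCLE, and nothing withholds the read from the treating clinician.

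The blinded video re-reads are also a partial defence. Three raters unaware of history and pathology review the videos, and their results are compared with cytology or histopathology. This weakens the circularity without removing it: they see the same video that informed the live read, and section 7 still uses the final diagnosis as reference.

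The size is assumed, and the examples move only benign nodules. Where a treated nodule is in truth malignant, the rule classifies it correctly. That stands too.

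Three stronger readings are tempting and not supported:

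- A reader might infer that the rule acts in the nCLE arm only. It applies to both arms, and control patients can also be treated without tissue. Only the part triggered by an nCLE read is specific to one arm.
- A reader might infer that the nCLE arm's yield is biased downward. If reads influence treatment, a benign-looking read could also avert it and raise the yield.
- A reader might infer that the primary comparison loses power. As shown, first-pass yield is largely spared.

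**Conclusion.** The concern holds as an open risk to the secondary accuracy results. The rule lets a treatment decision stand in for tissue in the reference, and the plan does not keep the nCLE read out of that decision. The expected distortion is upward for nCLE specificity and PPV and downward for ROSE/TBNA sensitivity and NPV. With about 30 benign nodules per arm, three patients are enough to move nCLE specificity by about 9 to 10 points and ROSE or TBNA sensitivity by about 7. These sizes rest on assumed counts, on every moved nodule being benign with a positive nCLE read, and, in the first example, on ROSE having no false positives. The documents do not show how often this would happen. The 12-month yield is exposed at 1.7 points per patient moved, net direction unknown. The correction is inexpensive and worth making before results are known.

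**What to change.** 1. Keep the conservative failure score for these patients in the yields of both arms.
2. For the nCLE and ROSE accuracy tables, flag patients treated without a confirmed diagnosis as reference-unconfirmed. Report their number by arm and, in the nCLE arm, by nCLE read.
3. Present the accuracy results twice, with all of them counted malignant and then all counted benign. Do not rely on leaving them out. If their nCLE reads are mixed, the two results need not bracket every possibility; the counts by read let the reader work out other allocations.
4. State that whoever assigns the study final diagnosis does so without the nCLE read.
5. Reconcile item 4 with the third endpoint, which as worded has the definitive diagnosis changing with nCLE, and with the statement that surgery does not depend on nCLE. One wording would judge changes in the intermediate diagnosis and recommendation against the masked final diagnosis.

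The cost is SAP and CRF wording, a little more analysis, and accuracy estimates reported as a wider range. Patient care is not altered.

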Microscopic, real-time image sequences are recorded, and cellular structures are visualized as desired. If at any time the ~3 mm Confocal Miniprobe™ protrusion interferes with the TBNA procedure, the Confocal Miniprobe™ can be pulled back into the needle by unlocking the purple screw to change directions, and then advanced again and locked. As long as the white screw remains locked, the Confocal Miniprobe™ cannot be advanced further than ~ 3mm beyond the distal needle tip and will not be damaged.

Retrieval of the probe

When the physician has completed imaging tissue with the Confocal Miniprobe™, it can be removed from the needle by unlocking the purple screw and extracting the probe. The locking device is a single-use device and is discarded after the procedure.

9. After imaging, extract the Confocal Miniprobe™ and locking device assembly from the needle	10. Remove the locking device from the Confocal Miniprobe™ and discard it
-----------------------------------------------------------------------------------------------	---------------------------------------------------------------------------

Further biopsies may then be performed with a 20 g needle, forceps, or brush per standard of care at the discretion of the bronchoscopist. After the biopsies, a bronchial-alveolar lavage may be performed per standard of care at the discretion of the bronchoscopist. Endobronchial ultrasound (EBUS) with lymph node biopsies will also be performed when indicated as part of the standard of care.

If a second lesion requires a biopsy, the bronchoscope will be withdrawn, and the chest will be imaged by fluoroscopy or chest ultrasound to rule out pneumothorax per standard of care. The bronchoscope can then be re-inserted, followed by navigation to the second lesion. However, only one lesion will be imaged with nCLE per patient.

After the Cellvizio® procedure

After removal of the Confocal Miniprobe™, the tissue can be routinely aspirated per the standard TBNA procedure and analyzed for chemistry, cytology, and/or tumor markers. nCLE imaging will not interfere with tissue / fluid specimen collection during the remainder of the conventional TBNA procedure.

Steps of standard - and study (in bold) procedures:

1. Patients will be sedated following standard procedure.
2. **(research-purposes) After starting the procedure, we will administer 2.5 ml of fluorescein 10% intravenously to visualize the CLE images only in the patients in the Robotic-nCLE-guided TBNA arm).**

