Based on investigator self-assessment, the proportion of cases in which the operator can successfully navigate to the lung target with Robotic guidance and Robotic-nCLE guidance will also be recorded and compared for both arms. Using a statistical test (Student T-test), the navigation success will be compared between arms (Robotic-guided TBNA and Robotic-nCLE-guided TBNA).

Navigation time

Total time that the locatable guide/ nCLE Confocal MiniprobeTM is used in the subject during the Robotic-guided TBNA or Robotic-nCLE-guided TBNA procedure. The navigation time medians and standard deviations will be calculated for both arms. Using a statistical test (Student T-test), they will be compared between arms (Robotic-guided TBNA and Robotic-nCLE-guided TBNA).

First- and cumulative-pass diagnostic yields and performance calculations

First-pass diagnostic yield was defined above (see section Sample size calculation for the definition). Two first-pass diagnostic yields will be calculated one for the Robotic-nCLE-guided TBNA arm and a second one for the Robotic-guided TBNA arm. 95% confidence intervals will be calculated, and the p-value to compare diagnostic yield values between the two arms. Sequential cumulative pass diagnostic yields will also be calculated for each arm.

The diagnostic performance of the sequential cumulative ROSE passes and the sequential cumulative nCLE passes for the Robotic-nCLE-guided TBNA arm and of ROSE only for the Robotic guided TBNA will also be assessed at the end of a follow-up period according to their sensitivities, specificities, positive predictive value (PPV), and negative predictive value (NPV). The sensitivity test will measure the ability of sequential cumulative ROSE passes or sequential cumulative nCLE passes to characterize malignant nodule (true positive rate) correctly. In contrast, the specificity test will measure the ability for sequential cumulative ROSE passes or sequential cumulative nCLE passes to correctly characterize benign nodule (true negative rate) using the final/definitive diagnosis as the reference.

Where a = true positive, b = false positive, c = false negative, and d = true negative:

- Sensitivity: Probability that sequential cumulative ROSE passes will be positive when malignancy is present (true positive rate): $= a/(a + c)$

- Specificity: Probability that a sequential cumulative ROSE passes will be negative when malignancy is not present (true negative rate): $= d/(b + d)$

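### For objective 5, cancer found anywhere in the lung can override a truly benign index nodule, so a correct nCLE or ROSE reading of that nodule is scored as a missed cancer

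*Combined protocol and SAP*

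**What the plan says.** Three parts of the combined protocol and SAP bear on this point.

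- **Section 5, Final Diagnosis or Definitive Diagnosis.** One sentence defines true negatives: "Cases with subsequent diagnostic tests confirming a non-malignant diagnosis or without lesion progression on radiographic follow-up will be considered true-negative at 12 months". A later sentence adds further triggers for a false negative, among them a "new diagnosis of cancer in the lung from any site (including non-index lesions or lymph nodes diagnosed as malignant by linear bronchoscopy", whether found during or after the index procedure. The section closes with a patient-level measure: "Twelve-month diagnostic yield will be calculated per subject as the rate of true-positives (for malignancy) plus true negatives (for malignancy").
- **Section 7, First- and cumulative-pass diagnostic yields and performance calculations.** This is the analysis for secondary objective 5, and its target is the nodule. Sensitivity is the ability of cumulative ROSE passes or "sequential cumulative nCLE passes to characterize malignant nodule (true positive rate) correctly". Specificity is the ability "to correctly characterize benign nodule (true negative rate) using the final/definitive diagnosis as the reference". The two techniques are then compared by the DeLong method "with the final diagnosis as the reference diagnosis".
- **Section 5, Retrieval of the probe.** The plan states that "only one lesion will be imaged with nCLE per patient". It also foresees other sampled sites: "If a second lesion requires a biopsy, the bronchoscope will be withdrawn" and re-inserted for that lesion, and lymph nodes are biopsied by EBUS when indicated.

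No reference confined to the index lesion is defined for the Section 7 accuracy analysis.

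**The concern.** The any-site trigger answers a question about the patient: did this work-up miss a lung cancer? Objective 5 asks about a nodule: did the reading at the needle tip describe the tissue there? The answers differ when the index nodule is truly benign and cancer is found at another site. The test then read its target correctly but is charged with a miss.

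The error can also run the other way. If nCLE wrongly calls such a nodule malignant while the biopsy is negative, the any-site label makes that wrong call a true positive.

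Section 5 also gives such a patient two labels. A nodule confirmed non-malignant meets the true-negative sentence, and the cancer elsewhere meets the false-negative sentence. Without a stated order, two analysts following the plan could build different 2x2 tables from the same data. With about 30 nodules in each class, a single patient moves the estimates visibly.

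**Working it through.** **The plan's own figures.** Section 4 gives 59 per arm for yields of 70% and 90%, 80% power and two-sided 0.05. With unpooled variance, n = (1.960 + 0.842)² × (0.7×0.3 + 0.9×0.1) / 0.2² = 7.85 × 0.30 / 0.04 = 58.9, so 59. The figure reproduces and does not depend on this point. Section 4 also assumes a prevalence of 0.5, and 59 × 0.5 = 29.5, which agrees with its expectation of at least 29 malignant nodules per arm.

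**Inputs for the illustration (nCLE arm).**
- 30 malignant and 29 benign index nodules: 59 patients split at the plan's prevalence.
- 27 of 30 malignant nodules detected: assumed.
- No false positives (specificity 100%): assumed.
- k patients with a truly benign index nodule and a cancer elsewhere: the documents give no rate, so k = 0 to 3 is shown.

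**Formulas (Section 7).** Sensitivity = a/(a + c) and NPV = d/(c + d). With an index-lesion reference, a = 27, c = 3 and d = 29. Under the any-site rule each of the k patients moves from d to c, so c = 3 + k and d = 29 − k.

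| k | Sensitivity | NPV |
|---|---|---|
| 0 | 27/30 = 90.0% | 29/32 = 90.6% |
| 1 | 27/31 = 87.1% | 28/32 = 87.5% |
| 2 | 27/32 = 84.4% | 27/32 = 84.4% |
| 3 | 27/33 = 81.8% | 26/32 = 81.3% |

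**Allowing false positives.** Take 29 malignant and 30 benign nodules with 90% sensitivity and 90% specificity at the index lesion (assumed). In expectation, 0.9k patients move from true negative to false negative and 0.1k from false positive to true positive.

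| k | Sensitivity | Specificity | PPV | NPV | Accuracy |
|---|---|---|---|---|---|
| 0 | 26.1/29 = 90.0% | 27/30 = 90.0% | 26.1/29.1 = 89.7% | 27/29.9 = 90.3% | 90.0% |
| 1 | 26.2/30 = 87.3% | 26.1/29 = 90.0% | 26.2/29.1 = 90.0% | 26.1/29.9 = 87.3% | 88.6% |
| 3 | 26.4/32 = 82.5% | 24.3/27 = 90.0% | 26.4/29.1 = 90.7% | 24.3/29.9 = 81.3% | 85.9% |

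In both tables each such patient costs about 2 to 3 points of sensitivity and about 3 points of NPV. Specificity keeps its expected value, because true negatives and false positives leave its denominator in proportion. PPV rises slightly.

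**Effect on the nCLE-ROSE comparison.** If both tests are negative on such a nodule, both acquire the same false negative. If nCLE is falsely positive and ROSE correctly negative, the any-site label reverses the scoring: nCLE gains a true positive and ROSE a false negative.

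**The case against.** **The true-negative sentence may already protect a proven-benign nodule.** This stands in part. The any-site trigger is introduced as an addition to the false-negative list, which favours reading it as the override, but the text does not settle the matter. The lack of precedence is therefore part of the point.

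**The any-site rule is a sound conservative choice.** This stands for the per-subject 12-month yield. The fault lies only in carrying the rule into an analysis of the nodule.

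**An index-only reference can err the other way.** A malignant lymph node may reflect a cancer missed in the index nodule, and a nodule without tissue would rest on imaging alone. This stands, and is why both references should be reported.

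**The shift is small against sampling error.** The exact 95% interval for 27/30 is 73-98%, and 82% lies inside it. This is true, but the shifts in sensitivity and NPV are systematic and would not shrink with more patients.

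**Stronger readings that the documents do not support.** A reader might infer that the image atlas and the video review are mislabelled too. Sections 5 and 7 compare the videos and frames with the corresponding cytology or histology, and the slides come from the measured nodules. A reader might infer that reproducibility suffers, but the planned statistic is Fleiss kappa between readers, which needs no truth label. Objective 8 mentions a reference standard, yet no analysis applies the any-site rule there. A reader might also expect biased specificity, and the calculation shows none in expectation.

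**Conclusion.** The concern holds for the objective 5 accuracy analysis of ROSE and nCLE. Followed as written, the any-site trigger gives the wrong truth label to a truly benign index nodule when cancer is found elsewhere, and Section 5 does not say whether that trigger or the true-negative sentence prevails. Under the stated assumptions (30 malignant, 29 benign, 27 of 30 detected, no false positives), one to three such patients lower sensitivity from 90% to 87-82% and NPV from 91% to 88-81%. The number of such patients is an assumption, and with none there is no effect.

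A reader might go on to infer that the primary first-pass yield is biased, since Section 4 asks a successful TBNA to match the final diagnosis and Section 8 makes the definitive diagnosis the reference for the endpoints. The documents do not establish this. They do not say how the any-site trigger would be applied to a single first pass, and any size would need rates that they do not give. The point concerns a secondary objective and can be settled by wording before analysis.

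**What to change.** 1. In Section 7, for the objective 5 analysis of cumulative ROSE and nCLE passes, define the reference at the index lesion: its own pathology, or its own follow-up where there is no tissue.
2. In Section 5, state which rule takes precedence when a case meets both the true-negative sentence and the any-site false-negative trigger.
3. Keep the any-site rule for the per-subject 12-month yield.
4. Report objective 5 under the any-site rule as a sensitivity analysis, with the number of patients whose label differs between the two references. This covers the case in which a malignant node reflects a cancer missed in the index nodule.

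The cost is SAP wording and one more tabulation. Section 6 already collects 12-month repeat procedures and new diagnoses on any nodule evaluated at the index procedure, and the sample size does not change. The drawback is that index nodules without tissue rest on imaging follow-up, so their number should be reported.
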